### 8.6.7 Blinding

Not applicable as being an open-label study.

### 8.6.8 Treatment Adherence

The IMP will be self-administered by the subjects as once daily oral tablets in the morning. At visit 3, 4, 5 and 6 (optional), subjects will return any empty and non-used treatments providing information to study personnel regarding their compliance with study medication. Compliance will be monitored by study personnel at the site by using the source documents and will be recorded in the eCRF.

Every visit after baseline will be used for dispensing new medication and collecting used medication in order to closely promote the treatment adherence.

### 8.6.9 Overdose

An overdose is defined as a known deliberate or accidental administration of investigational drug, to or by a study subject, at a dose above that which is assigned to the individual subject according to the study protocol.

All cases of overdose (with or without associated AEs) will be documented on an Overdose page of the eCRF, in order to capture this important safety information consistently in the database. Cases of overdose without manifested signs or symptoms are not considered AEs. AEs associated with an overdose will be documented on AE eCRF(s).

SAEs associated with overdose should be reported according to the procedure outlined in [Section 9.7.1](#).

In the event of drug overdose, the subject should be treated symptomatically.

### 8.6.10 Drug Accountability

The investigator or designee must document the receipt, dispensing, and return of IMP supplies and materials provided for this study in specific accountability forms included in the investigator's study file (ISF). The scanned copy of drug accountability forms will be retrieved from the study site by the responsible monitor, and the investigator will retain the original ones. Documentation of drug accountability for individual subjects will be captured in the eCRF.

The investigator or designee must ensure that the sponsor-supplied drug is used in accordance with the protocol and is dispensed only to subjects enrolled in the study. Upon receipt of sponsor-supplied drug, the investigator or designee must verify the contents of the shipments against the packing list. The verifier should ensure that the quantity is correct, and the medication is in good condition. If quantity and conditions are acceptable, they should acknowledge the receipt of the shipment (by signing the packing list and faxing or emailing per instructions provided on the form). If there are any discrepancies between the packing list and the actual product received, Linical must be contacted to resolve the issue. The packing list should be filed in the investigator's essential document file.

The investigator or designee must maintain 100% accountability for all sponsor-supplied drugs received and dispensed. Proper drug accountability includes, but is not limited to:

- Continuously monitoring expiration dates if expiry date is provided to the investigator or designee.
- Frequently verifying that actual inventory matches documented inventory.
- Verifying that the log is completed with the drug lot/patient number used to document each dose.
- Verifying that all containers used/assigned are documented accurately on the log.
- Verifying that required fields are completed accurately and legibly.

If any dispensing errors or discrepancies are discovered, the sponsor must be notified immediately.

Residual medication (complete blisters and boxes) must be returned to the sponsor, who will be responsible for accountability and destruction. If the site is responsible for destruction, the process must be done once the accountability is verified by the study monitor. The investigator is not permitted to dispense any study medication to persons not taking part in the study. Non-used drug will be returned to the center at visits 3, 4, 5, and 6 (optional), and compliance for prasugrel will be assessed as:

$$\text{Compliance (\%)} = \frac{(\text{Tablets dispensed}) - (\text{Tablets lost}) - (\text{Tablets returned})}{\text{Total number of days between visits}} \times 100$$

## 9.0 Adverse Events (AEs)

### 9.1 Definitions

#### 9.1.1 Adverse Event

An adverse event (AE) is defined as any unfavorable and unintended sign (including a clinically significant abnormal laboratory finding), symptom or disease, temporally associated with the use of a medicinal product, regardless of its nature, intensity, seriousness, or presumed relationship (causality) to the product or experimental procedure used.

Adverse Events will be collected since the informed consent signature, and all adverse events which occur after the first study medication intake and within 14 days after the treatment stop date will be considered as treatment emergent adverse events (TEAEs).

Each TEAE will be evaluated for duration, intensity, and relationship to (or association with) the study treatment (or other causes). Additionally, the actions taken (e.g., administration of treatment) and the resulting outcome of the adverse event will be indicated on the eCRF. All adverse events will be followed up until resolved or as clinically required.

Only subjects with an ongoing AE at the last study visit will be followed-up for safety reasons until the event is resolved or stabilized.

**Any AE, which remains unresolved after completion of the trial, requires detailed evaluation and follow-up until the AE has been resolved or a reasonable explanation for its persistence is found.**

If a worsening of any pathological condition that the subject had before the start of the study or medical problems that are present prior to the start of treatment but worsen during treatment occur, these must be considered as a new adverse event and will require a complete evaluation and the relevant explanation in the case report form.

#### 9.1.2 Additional Points to Consider for AEs

An untoward finding generally may:

- Indicate a new diagnosis or unexpected worsening of a pre-existing condition. (Intermittent events for pre-existing conditions or underlying disease should not be considered AEs.)
- Necessitate therapeutic intervention.
- Require an invasive diagnostic procedure.
- Require discontinuation or a change in dose of study medication or a concomitant medication.
- Be considered unfavorable by the investigator for any reason.
- AEs caused by a study procedure (e.g., a bruise after blood draw) should be recorded as an AE.

Diagnoses vs signs and symptoms:

- Each event should be recorded to represent a single diagnosis. Accompanying signs (including abnormal laboratory values or ECG findings) or symptoms should NOT be recorded as additional AEs. If a diagnosis is unknown, sign(s) or symptom(s) should be recorded appropriately as an AE(s).

Laboratory values and ECG findings:

- Changes in laboratory values or ECG parameters are only considered to be AEs if they are judged to be clinically significant (i.e., if some action or intervention is required or if the investigator judges the change to be beyond the range of normal physiologic fluctuation). A laboratory re-test and/or continued monitoring of an abnormal value are not considered an intervention. In addition, repeated or additional noninvasive testing for verification, evaluation or monitoring of an abnormality is not considered an intervention.
- If abnormal laboratory values or ECG findings are the result of pathology for which there is an overall diagnosis (e.g., increased creatinine in renal failure), the diagnosis only should be reported appropriately as an AE.

Pre-existing conditions:

- Pre-existing conditions (present at the time of signing of informed consent) are considered concurrent medical conditions and should NOT be recorded as AEs. Baseline evaluations (e.g., laboratory tests, ECG, X-rays etc.) should NOT be recorded as AEs unless related to study procedures. However, if the subject experiences a worsening or complication of such a concurrent condition, the worsening or complication should be recorded appropriately as an AE. Investigators should ensure that the event term recorded captures the change in the condition (e.g., “worsening of...”).
- If a subject has a pre-existing episodic condition (e.g., asthma, epilepsy) any occurrence of an episode should only be captured as a AE if the episodes become more frequent, serious or severe in nature, that is, investigators should ensure that the AE term recorded captures the change in the condition from Baseline (e.g., “worsening of...”).
- If a subject has a degenerative concurrent condition (e.g., cataracts, rheumatoid arthritis), worsening of the condition should only be captured as an AE if occurring to a greater extent to that which would be expected. Again, investigators should ensure that the AE term recorded captures the change in the condition (e.g., “worsening of...”).

Worsening of AEs:

- If the subject experiences a worsening or complication of an AE after starting administration of the study medication, the worsening or complication should be recorded appropriately as an AE. Investigators should ensure that the AE term recorded captures the change in the condition (e.g., “worsening of...”).
- If the subject experiences a worsening or complication of an AE after any change in study medication, the worsening or complication should be recorded as a new AE. Investigators should ensure that the AE term recorded captures the change in the condition (e.g., “worsening of...”).

Changes in severity of AEs:

- If the subject experiences changes in severity of an AE, the event should be captured once with the maximum severity recorded.

Preplanned surgeries or procedures:

- Preplanned procedures (surgeries or therapies) that were scheduled prior to signing of informed consent are not considered AEs. However, if a preplanned procedure is performed early (e.g., as an emergency) due to a worsening of the pre-existing condition, the worsening of the condition should be captured appropriately as an AE. Complications resulting from any planned surgery should be reported as AEs.

Elective surgeries or procedures:

- Elective procedures performed where there is no change in the subject's medical condition should not be recorded as AEs, but should be documented in the subject's source documents. Complications resulting from an elective surgery should be reported as AEs.

Insufficient clinical response (lack of efficacy):

- Insufficient clinical response, efficacy, or pharmacologic action, should NOT be recorded as an AE. The investigator must make the distinction between exacerbation of pre-existing illness and lack of therapeutic efficacy.

Overdose:

- Cases of overdose with any medication without manifested side effects are NOT considered AEs, but instead will be documented on an Overdose page of the eCRF. Any manifested side effects will be considered AEs and will be recorded on the AE page of the eCRF.

### 9.1.3 Serious Adverse Event

Serious adverse events are defined as any untoward medical occurrence that at any dose:

- result in subject's death.
- are life-threatening.
- result in permanent or significant disability/incapacity.
- cause hospital admission or prolong hospital stay.
- result in congenital anomalies or birth defects.
- medically important condition that may jeopardize the subject or may require intervention to prevent any of the outcomes listed above. Examples of such events are intensive treatment in an emergency room or at home for allergic bronchospasm; blood dyscrasias, or convulsions that do not result in hospitalization; or development of drug dependency or drug abuse.

NOTE: The term "life-threatening" in the definition of "serious" refers to any adverse event that places the subject, in the view of the investigator, at immediate risk of death from the event as it

occurred, i.e., it does not include an event that, had it occurred in a more severe form, might have caused death.

An overnight stay in the hospital that is only due to transportation, organization or accommodation problems and without medical background does not need to be handled/documentated as a SAE. Hospitalizations due to surgical procedures for pre-existing conditions that have been planned before enrolment of the subject are not considered SAEs.

#### 9.1.4 Unexpected Adverse Event

Any adverse event, which is not described in the Reference Safety Information (RSI) of the package insert (PI) in nature, severity or frequency is unexpected. Expectedness will be assessed in relation to the RSI of the PI. For details, please check the corresponding prasugrel / aspirin package inserts.

#### 9.1.5 Suspected Unexpected Serious Adverse Reaction (SUSAR)

A Suspected Unexpected Serious Adverse Reaction (SUSAR) is a suspected adverse reaction related to the treatment that is both unexpected and serious.

#### 9.2. Adverse Event Severity

Severity of adverse events will be classified according to the following criteria:

Mild	Discomfort noted, but no disruption of normal daily activity.
Moderate	Discomfort sufficient to reduce or affect normal daily activity.
Severe	Inability to work or perform normal daily activity

#### 9.3. Relationship to Study Drug

The causal relationship of an adverse event with the study medication will be established based on the following definitions:

Related	The AE follows a reasonable temporal sequence from study drug administration, and cannot be reasonably explained by the subject's clinical state or other factors (e.g., disease under study, concurrent diseases, concomitant medications). The AE follows a reasonable temporal sequence from study drug administration, and is a known reaction to the drug under study or its chemical group, or is predicted by known pharmacology.
Not related	The AE does not follow a reasonable temporal sequence from study drug administration, or can be reasonably explained by the subject's clinical state or other factors (e.g., disease under study, concurrent diseases, concomitant medications).

Any subject who is withdrawn from the study because of an AE will be followed until the outcome of the event is determined, and the investigator will prepare a written summary of the event and document the available follow-up information on the eCRF.

#### 9.4. Action Concerning Study Medication

- Drug withdrawn – a study medication is stopped due to the particular AE.
- Dose not changed – the particular AE did not require stopping a study medication.
- Unknown – only to be used if it has not been possible to determine what action has been taken.
- Not Applicable – a study medication was stopped for a reason other than the particular AE e.g., the study has been terminated, the subject died, dosing with study medication was already stopped before the onset of the AE.
- Dose Interrupted – the dose was interrupted due to the particular AE.

#### 9.5. Outcome

- Recovered/Resolved – Subject returned to first assessment status with respect to the AE.
- Recovering/Resolving – the intensity is lowered by one or more stages: the diagnosis or signs/symptoms has almost disappeared; the abnormal laboratory value improved, but has not returned to the normal range or to baseline; the subject died from a cause other than the particular AE with the condition remaining “recovering/resolving”.
- Not recovered/not resolved – there is no change in the diagnosis, signs or symptoms; the intensity of the diagnosis, signs/ symptoms or laboratory value on the last day of the observed study period has got worse than when it started; is an irreversible congenital anomaly; the subject died from another cause with the particular AE state remaining “Not recovered/not resolved”.
- Resolved with sequelae – the subject recovered from an acute AE but was left with permanent/significant impairment (e.g., recovered from a cardiovascular accident but with some persisting paresis).
- Fatal – the AEs which are considered as the cause of death.
- Unknown – the course of the AE cannot be followed up due to hospital change or residence change at the end of the subject’s participation in the study.

#### 9.6. Adverse Event Collection Period

Adverse events will be collected throughout the whole study period (screening of 4 weeks, treatment period 1 of 4 weeks, treatment period 2 of +24 weeks (optionally up to a maximum 12 months of P2Y12 inhibitor treatment after ACS underwent PCI), and safety follow-up if needed).

## 9.7. Adverse Event Reporting

All adverse events occurring during the trial must be documented in the CRF. This applies not only to those adverse events supposedly related to the study medication, but also to any undesired experience, whether or not a causal relationship is suspected.

For this, the CRF includes a specific section for collecting information related to the adverse events. In addition, for the serious adverse events, a standard Serious Adverse Event report form will be included.

### 9.7.1 Serious Adverse Events

All serious adverse events will be reported by the investigator to the monitor responsible for the clinical trial or to the Pharmacovigilance Manager at Linical within 24 hours after their knowledge. A Serious Adverse Event report form, with the minimal information related to the event, should be made available to the Pharmacovigilance Manager at Linical within 24 hours:

- a serious adverse event term (verbatim)
- an identifiable reporting source (at least name, site name, address and telephone number of the reporting investigator),
- suspected investigational medicinal product,
- an identifiable subject
- criterion of seriousness of the adverse event,
- the mandatory administrative information,
- Relationship with the study drug and a possible cause for the event

### 9.7.2 Non Serious Adverse Events

Non-serious adverse events will be documented in the specific section for reporting in the eCRF that will be submitted to Daiichi Sankyo Taiwan Ltd. once the participation of the subject in the clinical trial is completed.

## **10.0 Protocol Deviations**

### **10.1. Protocol Deviations**

Generally, a protocol deviation is not imperative for subject withdrawal. Before the statistical analysis begins, the protocol deviations must be taken into account for the population analysis. The mandatory withdrawal reasons will be considered as major protocol deviations. Other protocol deviations will be classified as minor protocol deviations. Additionally, the following major protocol deviations will be considered:

- 1) Violation of one of the inclusion/exclusion criteria after enrolment into the study.
- 2) Treatment incorrectly administered, or overdose.

Any protocol deviation must be recorded in the eCRF.

### **10.2. Procedure for protocol amendments**

Any amendment to this protocol involving a substantial change may be made as an amendment or addendum in writing. In order to be formalized, it is necessary to obtain the agreement of all the responsible people who signed the original protocol.

Amendments that can result in substantial changes in the original protocol must be submitted and approved by the IRB/IEC.

## 11.0 Statistical Methods and Determination of Sample Size

### 11.1. Statistical and analytical plans

The statistical analysis will be performed by the Department of Biostatistics of Linical, using SAS® version 9.4 or later.

Statistical significance will be assessed for two-sided probability values  $< 0.05$ .

All descriptive variables will be tabulated. Quantitative variables will be described showing their number of available and missing observations, mean, median, standard deviation (SD), the range (minimum and maximum) and the first and third quartiles. Frequency and percentage will describe qualitative variables. Missing values will be tabulated with their frequency but will not be included in the calculation of percentages.

The main population for both the efficacy (antiplatelet effect) and the safety analysis will be the safety population (SAF), defined as all the subjects who have received at least one dose of study treatment. A Per Protocol (PP) population, defined as all the subjects of the safety population who do not perform any major protocol deviation

Full details of the statistical analysis will be given in a Statistical Analysis Plan (SAP) which will be prepared, approved and signed before the database closure, and so before the subjects' evaluability assessment.

Any deviation from the original SAP will be included and reported in the clinical study report (CSR).

#### 11.1.1 Data Sets Analyzed

The safety population (SAF) will be defined as all subjects who have received at least one dose of the study treatment.

The per protocol population (PP) will be defined as all subjects in the SAF who do not experience a major protocol deviation.

#### 11.1.2 Demographic and Other Baseline Characteristics

Baseline characteristics (gender, age, race, weight, height, body mass index, blood pressure, heart rate) for the safety population will be summarized descriptively.

Categorical data will be summarized with absolute and relative frequencies (percentage), and numerical data will be summarized with the number, mean, median, standard deviation (SD), the range (minimum and maximum), and the first and third quartiles (if applicable).

### 11.1.3 Efficacy Analyses

#### 11.1.3.1 Primary Efficacy Analyses

##### 11.1.3.1.1 PERIOD 1 (4 weeks)

Mean change in the P2Y12 reaction unit (PRU) value assessed with VerifyNow® from baseline to the end of the 4-week MD treatment period, after switching from clopidogrel MD to prasugrel MD will be analyzed with a paired t-test model. Mean changes will be presented with their corresponding 95% confidence interval.

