## 7.2. Discussion of Study Design, including the Choice of Control Groups

This trial is designed as a phase 4, multicenter, non-comparative, open label, 28 weeks (optionally up to a maximum 12 months of P2Y12 inhibitor treatment after ACS underwent PCI) switching study in subjects with a previous diagnosis of Acute Coronary Syndrome (ACS) who had undergone Percutaneous Coronary Intervention (PCI) and were treated with either (a) clopidogrel maintenance dose (MD) of 75 mg once daily and aspirin 81-100 mg per day for 2-8 weeks following clopidogrel loading dose (LD) of 300 mg or 600 mg at the time of PCI; or (b) ticagrelor MD of 90 mg bid and aspirin 81-100 mg per day for 1-4 weeks and switching to clopidogrel maintenance dose (MD) of 75 mg once daily and aspirin 81-100 mg per day for 2-4 weeks (either directly or via clopidogrel loading dose [LD] of 300 mg or 600 mg) following ticagrelor LD of 180 mg at the time of PCI; or (c) clopidogrel maintenance dose (MD) of 75 mg once daily and aspirin 81-100 mg per day for 2-8 weeks following ticagrelor LD of 180 mg at the time of PCI; or (d) based on investigator's judgement with at least 2 weeks continues use of clopidogrel MD and aspirin 81-100 mg per day before switching to prasugrel and maximum 8 weeks P2Y12 inhibitors MD treatment (prasugrel is not allowed).

The prasugrel MD dose for this study (3.75 mg once daily) has been selected based on the package insert DSTW 201803-03, Daiichi Sankyo Taiwan Ltd. The investigator's discretion will be followed for deciding on aspirin dosing as far as continuing the dual antiplatelet therapy (DAPT) may increase the risk of gastrointestinal bleeding; therefore adverse events management related to aspirin doses will be managed as per the investigator's criteria for this and any other criteria based on medical judgement.

The P2Y12 reaction unit (PRU) assessed with VerifyNow® has been selected for the evaluation of the study primary endpoint because this is one of the most user-friendly point-of-care (POC) platelet function test systems because it produces rapid results at the patient bed-site, and the VerifyNow platform consists on a validated tool which has currently three types of single-use,

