### 8.5.2 Discontinuation or Withdrawal of Individual Subjects

If a subject having received the 1st prasugrel MD treatment terminates the study prematurely for any reason, all attempts should be made by the investigator to perform the procedures for the early termination visit (same as for the week 28 visit) and determine the primary reason for the termination and where possible the primary underlining reason, providing as much as detail as possible, and documenting the information on the eCRF. .

For subject who terminated before Visit 3, Platelet function tests have to be conducted during the early termination visit.

The primary reason for discontinuation or withdrawal of the subject from the study should be noted using the following categories:

- (1) Adverse Event (AE). The subject has experienced an adverse event that requires early termination because continued participation imposes an unacceptable risk to the subject's health or the subject is unwilling to continue because of the adverse event or pre-treatment adverse event.
- (2) Noncompliance with investigational medicinal product (IMP) prasugrel MD + aspirin.  
Period 1 compliance is defined as 80% compliance in the first 4 weeks with maximum 2 consecutive missed doses in the last week.  
Period 2 compliance is defined as 80% compliance in the 24 weeks (up to 12 months, alternatively)
- (3) Major protocol deviation. The subject failed to meet protocol entry criteria or did not adhere to protocol requirements, and continued participation poses an unacceptable risk to the subject's health, or a major protocol deviation occurred at the site.
- (4) Withdrawal of consent. The subject (or subject's legally acceptable representative) wishes to withdraw from the study. The reason for withdrawal, if provided, should be recorded in the case report form (eCRF). Subjects may withdraw from the study at any time at their own request without giving reasons and without any disadvantageous consequences for their subsequent medical care.
- (5) Lost to follow-up. The subject did not return to the clinic and attempts to contact the subject were unsuccessful. Attempts to contact the subject must be documented.

(6) Other.

In the case of study termination by the sponsor, institutional review board (IRB), independent ethics committee (IEC), or regulatory agency, reason for withdrawal should be captured as Other, Study Termination.

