## 11.2. Determination of sample size

A total of 200 patients will be enrolled to have 170 completed patients in the study (expected drop-out rate of 15%).

The proposed total sample size of 170 completed patients will allow to estimate a mean PRU value with a precision of around 10% and a confidence level of 95%, considering a standard deviation of 70 (Han-Young Jin, 2014).

The probability that 1 or more adverse reactions (or other events) will occur in a sample of 170 patients with an anticipated incidence rate of 0.01 is 0.82%. So this sample achieves a power of 82% to find adverse events with incidences close to 0.01.

This sample size will also permit enough power to detect a statistically significant reduction of the P2Y12 ( $\neq 0$ ), considering an effect size around 0.40 ( $\mu=30$ ,  $SD=70$ ), using a significance level of 0.05 and a two-sided one-sample t-test.

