### **11.5. Handling of dropouts or missing data**

As a general approach, no missing data imputation is planned for the study; however, it will be further concreted in the Statistical Analysis Plan (SAP).

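### The primary PRU analysis is declared on the safety population, but the paired t-test uses only subjects with two PRU values; the possible bias is small, and a two-visit model would limit it at almost no cost

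*Combined protocol and SAP*

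**What the plan says.** - **Test.** Section 11.1.3.1.1 says that the mean PRU change from baseline to the end of the 4-week period "will be analyzed with a paired t-test model", with a 95% confidence interval.
- **Population.** Section 11.1: "The main population for both the efficacy (antiplatelet effect) and the safety analysis will be the safety population (SAF". Section 11.1.1 defines that set as "all subjects who have received at least one dose of the study treatment". Neither section requires a PRU value.
- **Missing data.** Section 11.5, as a general approach: "no missing data imputation is planned for the study; however, it will be further concreted in the Statistical Analysis Plan (SAP". No separate SAP text is in the documents.
- **Early termination.** Section 8.5.2: "For subject who terminated before Visit 3, Platelet function tests have to be conducted during the early termination visit". Footnote 9 of the schedule in Appendix 18.1 repeats this. Neither place says whether that value is used as the Week 4 value.
- **Sample size.** Section 11.2: "A total of 200 patients will be enrolled to have 170 completed patients in the study", at an expected drop-out of 15%. No loss rate to Week 4 is given.
- **Visibility.** The study is open label (Section 8.6.7). Section 7.2 chooses the assay partly because "it produces rapid results at the patient bed-site". No rule withholds the Day 1 result from the investigator.

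**The concern.** The declared population and the test do not describe the same subjects. A paired t-test needs two values per subject. Without imputation, a treated subject with a Day 1 PRU and no later PRU is left out, although the Day 1 value is known and informative. The set analysed is then SAF subjects with both PRU values, and the plan does not say so.

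This matters for the estimate if the excluded subjects differ in Day 1 PRU. Change from baseline is usually correlated with baseline, so selective loss by Day 1 PRU moves the mean change away from its value in the SAF. An open-label design with a bedside result makes such dependence possible. The plan names no missing-data assumption and no sensitivity analysis for missing PRU. The per-protocol set does not fill the gap, because it removes subjects and recovers none.

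**Working it through.** **The plan's own figures.** 200 × (1 − 0.15) = 170, so the enrolment figure reproduces. With an effect size of 0.40 (the plan's rounding; 30/70 = 0.43), a two-sided 0.05 one-sample t-test has power 0.999 at n = 170 and 0.977 at n = 100. Missing pairs are therefore a matter for the estimate and its interval, not for power.

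**Inputs from the documents.** SD 70 and mean change 30 (Section 11.2). The plan does not say whether 70 is the SD of the value or of the change. I apply it to the PRU value at both visits; at correlation 0.5 the SD of the change is then also 70, because 70 × √(2 × (1 − 0.5)) = 70.

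**Assumed inputs.** Correlation ρ between visits of 0.3 to 0.7, the fraction d of pairs missing, and how loss depends on Day 1 PRU. The documents give none of these.

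**Missing pairs by Week 4.** The 15% covers the whole study. If it accrued evenly over 28 weeks, the share by Week 4 would be 15% × 4/28 = 2.1%. At a constant hazard it would be 1 − 0.85^(4/28) = 2.3%. At the late edge of the Visit 3 window (Day 42) it would be 1 − 0.85^(42/196) = 3.4%. I use 2-5%, before crediting any early-termination PRU.

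**Bias formula.** With equal SDs and loss depending only on Day 1 PRU:

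bias in mean change = (ρ − 1) × (mean Day 1 PRU of retained subjects − mean Day 1 PRU of all SAF)

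It is zero if loss is unrelated to Day 1 PRU, or if ρ = 1.

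**Shift in the retained Day 1 mean.**
- Pattern A: the odds of loss double per SD of Day 1 PRU. The shift comes from integrating over a normal baseline.
- Pattern B: all losses fall at random within one outer third. The mean of that third lies 1.091 SD from centre, so the shift is 70 × 1.091 × d/(1 − d). At d = 0.05 this is 76.4 × 0.0526 = 4.02 PRU.

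**Absolute bias in PRU (ρ = 0.7 / 0.5 / 0.3).**

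| Pairs missing | Pattern A | Pattern B |
|---|---|---|
| 2% | 0.3 / 0.5 / 0.7 | 0.5 / 0.8 / 1.1 |
| 5% | 0.7 / 1.2 / 1.6 | 1.2 / 2.0 / 2.8 |
| 15% | 2.0 / 3.4 / 4.8 | 4.0 / 6.7 / 9.4 |

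If low Day 1 values are lost, the fall is overstated. If high values are lost, it is understated by the same amount.

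**Outer bound.** If every loss came from the very end of the Day 1 distribution, the bias would be 2.3 / 3.8 / 5.3 PRU at 5% and 5.8 / 9.6 / 13.4 PRU at 15%. Nothing in the documents suggests such a pattern.

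**Scale.** With SD of change 70 and n = 170, the standard error of the mean change is 70/√170 = 5.4 PRU.

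**Simulation check (n = 200, ρ = 0.5, high values lost, 4,000 runs).** Under pattern A at 5% loss, the paired estimate was off by 1.25 PRU and its 95% interval covered the true value in 94.0% of runs. At 15% loss the figures were 3.4 PRU and 90.9%. An estimate that uses the Day 1 values of all subjects was within 0.15 PRU of the truth in every pattern run. With loss unrelated to Day 1 PRU, the paired t-test was unbiased (coverage 94.8%).

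**The case against.** The strongest reply is that the problem may be close to nil. A paired t-test is a standard analysis of a single-arm change between two visits. A decision to stop before Visit 3 triggers a termination visit with platelet function testing, so the losses that a visible PRU could drive are those for which a second value is required. PRU is not among the withdrawal reasons in Section 8.5.2, and no passage ties stopping to it. Section 11.5 is provisional and leaves detail to the SAP.

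Most of this stands, and it rules out three stronger readings that a reader might infer.

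- **That the estimate is for completers only.** Early terminators can have two values.
- **That 15% of pairs will be missing at Week 4.** Section 11.2 gives 15% for the whole study, and a subject lost after Visit 3 has both values.
- **That the result is biased in a known direction.** Low-baseline and high-baseline loss give opposite signs, and the documents support neither over the other.

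Two things remain. Deaths, lost subjects and missed termination visits still leave a single value. The endpoint is defined at the end of the 4-week period, so an early-termination PRU may or may not count. If it does not, early terminators drop out as well. Deferral to a SAP does not settle either matter; it shows where the answer belongs.

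**Conclusion.** The point holds as a low-severity gap. The effective primary analysis set is SAF subjects with both PRU values. The plan does not say this, and it does not say what the early-termination PRU is for. Any bias is conditional on loss depending on Day 1 PRU, which the open-label bedside assay makes possible and the documents do not show.

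Under patterns A and B with 2-5% missing pairs, SD 70 and ρ from 0.3 to 0.7, the bias is about 0.3-3 PRU on a planned 30, below one standard error. Values of about 4-10 PRU arise under pattern B only if the full 15% were lost before Week 4 and confined to one baseline third. A reader might infer that the primary test itself is unsafe. It is not: power is about 0.999 at n = 170, and a shift of this size would not overturn a 30 PRU effect.

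**What to change.** In Section 11.1.3.1.1 and the SAP:

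1. Estimate the change with a repeated-measures model: Day 1 and Week 4 PRU both as outcomes, visit as the only fixed effect, unstructured 2 × 2 covariance, REML. Fit it to all SAF subjects with at least one PRU value, and report the visit difference with its 95% interval.
2. Keep the paired t-test as a sensitivity analysis.
3. State whether the early-termination PRU enters as the Week 4 value.
4. Report the number of complete pairs beside the SAF count.

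The cost is a few lines of SAP text and one standard model call in the software already named. No new data are needed, and with complete data the model gives the same estimate as the paired t-test. The downside is that it relies on a missing-at-random assumption, which should be stated. It does not correct loss driven by unobserved events after Day 1.
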